5.7 Withdrawal Criteria

Subjects may withdraw from the clinical investigation at any time without providing a reason. Subjects will not be penalized nor lose any benefits to which they are otherwise entitled if they should choose to withdraw. The Investigator may also choose to withdraw the subject if he or she feels that this is in the subject's best interest.

The possible situations for subject withdrawal will be managed as such:

- Subjects who withdraw from the study after receiving investigational device will be followed for safety through the end of the study if they agree. Efforts will be made to collect any final data and information regarding the reason for withdrawal. Data collected prior to withdrawal from the study may be used in in study analyses; or
- Subjects who withdraw from the study before receiving investigational device receive routine care. No study-specific safety or efficacy assessments will be conducted.

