7 ADVERSE EVENTS

7.1 General

An adverse event (AE) is defined according to the European Standard EN ISO 14155 as ‘any untoward medical occurrence in a subject’. An adverse event related to a device is defined as an ‘adverse device effect’ (ADE) and is defined as ‘any untoward and unintended response to an investigational medical device’.

An adverse event or an adverse device effect may be mild, moderate or severe and are usually unexpected.

A device deficiency is defined as the inadequacy of a medical device with respect to its identity, quality, durability, reliability, safety or performance, which may include device malfunctions, use errors and inadequate labeling.

All adverse events, adverse device effects, and or device deficiencies, either observed by the Principal Investigator or reported by the subject, must be reported to the Sponsor/Sponsor representative. To report an adverse event or adverse device effect or device deficiency, the Principal Investigator will complete an adverse event report form or relevant form located in the Case Report Form. The report will include the following information: nature, severity, date of onset, duration, course and history of the adverse event/adverse device effect and causality. The subject will be questioned about any adverse event(s) and adverse device effect(s) at each visit.

Expected adverse events and anticipated adverse device effects are included in Section 13.

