7.2 Adverse Event Documentation

Adverse events will be documented by the Principal Investigator on the appropriate source document(s) at the investigational site and also on the Adverse Event CRF. Adverse events are to be recorded and dated according to when they are first observed. The subsequent treatment(s) should also be documented. The following will be recorded on the Adverse Event CRF:

- Accepted medical term for the event;
- Description of the event;
- Date of onset;
- Date of resolution, if applicable;
- Outcome;
- Treatment(s)/action(s) taken;
- Severity;
- Relationship to the investigational device; and
- Determination of reportability (see Reporting Section below).

The severity of the event will be determined by the Principal Investigator using the following definitions:

- Mild: the symptoms are transient, barely perceptible by the subject and do not hinder normal activity; no treatment is usually prescribed to reduce these symptoms;
- Moderate: the symptoms are sufficiently severe to provoke discomfort in the subject and sufficiently uncomfortable to prevent normal activity; a treatment may be required; or
- Severe: the symptoms considerably modify the normal course of the subject’s activities or are disabling or are life-threatening; the treatment studied should be suspended; a treatment for the symptoms is prescribed.

The relationship to the investigational device will be determined by the Principal Investigator using the following definitions:

- Not related: the adverse event is due to the underlying disease state or is due to concomitant medications or therapy not related to the use of the device;
- Possibly related: the adverse event has a reasonable temporal relationship to the use of the device but alternative etiology is equally or more likely compared to the potential relationship to the use of the device;
- Probably related: the adverse event has a strong temporal relationship to the use of the device and alternative etiology is less likely compared to the potential relationship to the use of the device; or
- Definitely related: the adverse event has a strong temporal relationship to the use of the device, follows a known response pattern and cannot reasonably be explained by known characteristics of the subject's clinical state or other therapies.

The expectedness of the adverse event will be determined by the Principal Investigator as:

- Anticipated; or
- Unanticipated.

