8 INDEPENDENT DATA MONITORING COMMITTEE

An Independent Data Monitoring Committee (IDMC) will be formed to review data from the clinical investigation to evaluate the safety and efficacy of the investigational device. The IDMC will be formed prior to subject enrollment and the names, affiliations, and academic backgrounds of all members will be provided to the Regulatory/Competent Authority.

The members of the IDMC are responsible for safeguarding the interests of study participants, assessing the safety and efficacy of study procedures, and reviewing the overall conduct of the clinical investigation. The IDMC will review clinical investigation data to evaluate study conduct, investigational device safety, and scientific validity and integrity of the investigation.

The IDMC will provide recommendations regarding the implementation and progress of clinical investigation, including continuation, suspension and/or termination of the clinical investigation. A separate charter for the IDMC will define and describe:

- Roles and responsibilities;
- Membership;

- Frequency of meetings; and
- Documentation and reporting.

A separate CEC (Clinical Events Committee) will be formed to review all SAEs and corresponding data for each SAE. The CEC will be formed prior to subject enrollment and the names, affiliations, and academic backgrounds of all members will be provided to the Regulatory Authority.

The members of the CEC will be responsible for reviewing and adjudicating SAEs for relatedness to the hemostatic device and expectedness. A separate charter for the CEC will define and describe:

- Roles and responsibilities;
- Membership;
- Frequency of meetings;
- Adjudication process; and
- Documentation and reporting.

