10 TERMINATION OF THE CLINICAL INVESTIGATION

10.1 Subject Withdrawals and Discontinuation

During the course of this clinical investigation, subjects will be or may elect to withdraw from investigation participation for any of the following reasons:

- Subject's withdrawal of consent;
- Any unexpected adverse device effect which is, in the opinion of the Principal Investigator, related to the device and will endanger the well-being of the subject if the treatment is continued;
- The development of any undercurrent illness(es), infection(s) or condition(s) that might interfere with the Clinical Investigational Plan; or
- Any problem deemed by the Principal Investigator and/or Sponsor to be sufficient to cause discontinuation.

All subjects discontinued from the clinical investigation due to an UADE, directly related to the clinical investigation, will be treated until the effect resolves. The Principal Investigator will clearly document the date and reason(s) for subject withdrawal in Discontinuation CRF.

Subjects who are withdrawn will not be replaced if they have received the investigational or control device. If possible, any procedures or assessments planned for the subject on withdrawal from the clinical investigation should be performed when intention to withdraw the subject is announced.

Subjects who are withdrawn prior to receiving investigational or control device will be replaced.

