5 ABBREVIATIONS AND DEFINITIONS

Abbreviation / Term	Definition
ADE	Adverse Device Effect - any untoward and unintended response to an investigational medical device
AE	Adverse Event - any untoward medical occurrence in a subject
CRF	Case Report Form
eCRF	Electronic Case Report Form
Enrolled	A subject is enrolled when he/she meets all preoperative inclusion/exclusion criteria, signs the informed consent form, and meets the intraoperative eligibility criteria.
IDE	Investigation Device Exemption
IDMC	Independent Data Monitoring Committee
IFU	Instructions for Use
SADE	Serious Adverse Device Effect – an adverse device effect that has resulted in any of the consequences characteristic of a serious adverse

	event or that might have led to any of these consequences if suitable action had not been taken or intervention had not been made or if circumstances had been less opportune
SAE	Serious Adverse Event – an adverse event that: 
 • Led to death • Led to a serious deterioration in the health of the subject, that either resulted in a life-threatening illness or injury, or a permanent impairment of a body structure or a body function, or in-patient hospitalization or prolongation of existing hospitalization, or resulted in medical or surgical intervention to prevent life-threatening illness or injury or permanent impairment to a body structure or a body function • Led to fetal distress, fetal death or a congenital abnormality or birth defect
SAP	Statistical Analysis Plan
SBSS	Surface Bleeding Severity Scale
TBS	Target Bleeding Site
UADE	Unanticipated Adverse Device Effect – any serious adverse effect on health or safety, any life-threatening problem or death cause by, or associated with a device, if that effect, problem, or death was not previously identified in nature, severity or degree of incidence in the study protocol; or any other unanticipated serious problem associated with a device that relates to the rights, safety, or welfare of subjects

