10.6.2 Analytic Methods

Endpoints used to characterize the safety profile include the rate of occurrence of all AEs and SAEs, reoperation rate due to bleeding, mean volume of intraoperative transfusions, total operative time, mean

duration of hospitalization, intraoperative blood product administration, and post-operative blood product administration.

Summaries of the number and percent of subjects with at least one SAE will be provided. Comparisons of the proportion of subjects experiencing SAEs will be made between treatment arms. Summaries of the number of percent of AEs will also be provided for each treatment arm.

Differences in mean overall blood loss, mean volume of intra-operative transfusions, mean total operative time, and mean duration of hospitalization will be estimated using linear regression models with stratified adjustment for surgery type and separated by surgery type. In all cases, the robust variance estimator will be used and a 95% Wald-based interval will be computed. Comparisons of the incidence of re-operation (total and reoperation due to bleeding) and the incidence post-surgery bleeding complications will be made using a general linear model to estimate the difference in the probability of each outcome after stratified adjustment for surgery type. Comparisons of the incidence of re-operation and the incidence post-surgery bleeding complications within each surgery type will be made using an exact two sample binomial test of proportions.

For binary endpoints, the proportion and corresponding 95% scored-based confidence interval will be computed. The proportion of UADEs or SADEs will also be computed and a 95% scored-based confidence interval will be computed for the true UADE or SADE rate. In the event that no UADEs or SADEs are observed, the upper bound of the 95% confidence interval will be based upon the exact binomial distribution.

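### Investigator-assessed relatedness, ADE/SADE and post-withdrawal follow-up are worded for HEMOBLAST only, and the UADE/SADE proportion has no stated arm or denominator

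*Protocol*

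**What the plan says.** The protocol keeps its device terms apart. The Synopsis lists HEMOBLAST as the investigational device and G+T as the comparator, and Section 3.5 again identifies HEMOBLAST as the investigational device. Where both are meant, the text names both, as in Section 10.1: "Subjects who are withdrawn will not be replaced if they have received the investigational or control device". Section 11 does the same for the use of data from withdrawn subjects.

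Three provisions name the investigational device alone:

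- **Causality.** The Adverse Event CRF field listed in 7.2 asks for relationship to the investigational device, and the lead-in to the categories reads "The relationship to the investigational device will be determined by the Principal Investigator using the following definitions".
- **ADE and SADE.** Protocol 7.1 defines an ADE as "any untoward and unintended response to an investigational medical device". SAP Section 5 repeats it: "Adverse Device Effect - any untoward and unintended response to an investigational medical device". Section 7.3 defines a SADE as an ADE with serious, or potentially serious, consequences, so SADE inherits the limit.
- **Withdrawal.** Section 5.7 gives post-withdrawal safety follow-up to those who received the investigational device. For the rest it says "Subjects who withdraw from the study before receiving investigational device receive routine care" and rules out study-specific assessments.

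Two provisions are broader. The UADE definition in 7.3 refers to a device without saying which. The Clinical Events Committee (CEC) in Section 8 is charged with "reviewing and adjudicating SAEs for relatedness to the hemostatic device and expectedness".

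On analysis, SAP 10.6.2 states "The proportion of UADEs or SADEs will also be computed" with a 95% interval, and an exact upper bound if no event occurs. It gives no arm or denominator. SAP 10.6.1 sets the safety population as treated subjects of both arms plus lead-ins. SAP 10.2 bases data summaries on the intervention received.

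**The concern.** The stated objective is safety compared with G+T, and Section 3.3 justifies the control partly by its similar risk profile. A comparison of device-related events needs the same causality question in both arms. Here the investigator is asked about a device that control subjects never receive, while the CEC is asked about the hemostat in general. The same serious control-arm event can therefore be judged under two different scopes, and a non-serious one is never judged against G+T at all.

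The classification also drives reporting. Under 7.3, SADEs and UADEs are followed to resolution with information sent to the sponsor's representative. For other SAEs, that information stops at study discontinuation. An unresolved serious reaction to G+T that is classed as neither would be reported for a shorter time than the same reaction to HEMOBLAST.

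The UADE/SADE proportion then has a numerator that is unequal between arms and a denominator that is not given.

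**Working it through.** **1. What happens to a reaction to G+T, followed as written**

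| Control-arm event | Investigator form (7.1, 7.2) | UADE (7.3) | CEC (Section 8) |
|---|---|---|---|
| Non-serious | No relatedness to G+T recorded; not an ADE | Not applicable | Not reviewed |
| Could have become serious but did not | Not an ADE, so not a SADE | Only if it meets the UADE terms | Not reviewed unless an SAE |
| Serious, anticipated | Not a SADE | Not applicable | Can be attributed to G+T |
| Serious, unanticipated | Not a SADE | Can be captured | Can be attributed to G+T |

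The individual categories in 7.2 speak simply of the device, but they sit under a lead-in that names the investigational one.

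**2. Withdrawal**

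Section 5.7 draws its line at receipt of the investigational device. Sections 10.1 (replacement) and 11 (use of data) draw it at receipt of either device. A treated G+T subject who withdraws is on the untreated side in 5.7 and on the treated side in 10.1 and 11.

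**3. The planned population**

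Protocol 6.4.2 gives 267 HEMOBLAST, 133 G+T and at most 50 lead-ins, all on HEMOBLAST. The sum is 267 + 133 + 50 = 450, which reproduces the stated maximum Full Analysis Population. Subjects exposed to HEMOBLAST number 267 + 50 = 317. The G+T share is 133/450 = 29.6%.

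**4. If the proportion were pooled and only HEMOBLAST events counted**

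For x events, the pooled rate divided by the exposed rate is (x/450)/(x/317) = 317/450 = 0.704, which is 29.6% too low.

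With zero events, the exact two-sided 95% upper limit is U = 1 − 0.025^(1/n):

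- n = 450: 0.82%
- n = 317: 1.16%

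Score intervals for assumed counts:

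| Events | Over 450 | Over 317 |
|---|---|---|
| 3 | 0.67% (0.23 to 1.94) | 0.95% (0.32 to 2.75) |
| 6 | 1.33% (0.61 to 2.88) | 1.89% (0.87 to 4.07) |

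**5. Sensitivity to enrolment**

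- No lead-ins: ratio 267/400 = 0.668; zero-event limits 0.92% pooled against 1.37% exposed.
- Stop at the interim (160 HEMOBLAST, 80 G+T) with 50 lead-ins: ratio 210/290 = 0.724; limits 1.26% against 1.74%.

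**6. If the proportion were split by arm**

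The HEMOBLAST denominator is then right, but investigator-classified G+T SADEs are undercounted. An artefactual 0/133 would be reported with an exact upper limit of 1 − 0.025^(1/133) = 2.74%, and that interval would not reflect reactions left unclassified.

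**The case against.** The best reply is that the restriction is loose drafting. Section 7.1 opens the ADE sentence generically ("An adverse event related to a device is defined as an"), the UADE definition is not tied to HEMOBLAST, and the CEC adjudicates every SAE for the hemostat used. Section 11 puts those adjudications in the final report. Section 13, where 7.1 places anticipated device effects, also mentions G+T risks. A reader might infer that G+T subjects can never have a device-related event. The documents do not support that: serious G+T events can be identified through the CEC or as UADEs. What remains is investigator attribution, which matters most for non-serious events and for SADEs that are not SAEs.

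A reader might also infer that the SAP pools unexposed controls into the UADE/SADE rate. It does not say so. Summaries by intervention received (SAP 10.2), and the by-arm treatment of AEs and SAEs in 10.6.2, point the other way. The fair criticism is that the denominator is unstated.

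The planned between-arm safety comparisons (SAEs, reoperation, bleeding, blood loss, transfusion, operative time, stay) do not use relatedness, so they are unaffected. The CRF itself is a separate document that was not available. These points limit the consequence, but they do not supply a G+T relatedness item.

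On withdrawal, 6.6 applies follow-up to all subjects, and 10.1 asks for planned assessments when withdrawal is announced. The conflict in 5.7 is therefore one of wording and does not show an intended difference between arms.

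**Conclusion.** The point stands as an inconsistency of device scope plus an unspecified estimate. Investigator causality, ADE and SADE, and the 5.7 withdrawal rule cover HEMOBLAST only, while UADE, CEC review, 10.1 and 11 cover either device. The protocol's consistent use of its terms makes it hard to read this as shorthand.

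The size depends on a choice that the SAP leaves open. With pooling and no G+T event counted, the rate is 29.6% too low and the zero-event limit is 0.82% instead of 1.16%, at full enrolment with 50 lead-ins. In the other enrolment scenarios above, the shortfall runs from about 28% to 33%. With a split by arm there is no dilution, but the investigator-classified G+T count is too low by an amount that the documents cannot give. The primary efficacy analysis is not touched. The change should be made, because it removes an asymmetry between arms in safety ascertainment and in a planned estimate.

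**What to change.** - **Protocol 7.1 and 7.2, the Adverse Event CRF and SAP Section 5:** record relatedness, and apply ADE and SADE, to the study hemostat received (HEMOBLAST or G+T) in both arms, in line with the CEC's remit.
- **SAP 10.6.2:** report ADE, SADE and UADE proportions and limits by device received, with only subjects exposed to that device in the denominator. State whether lead-ins are included in the HEMOBLAST figure.
- **Protocol 5.7:** reconcile with 10.1 and 11 so that withdrawn subjects treated with either device are handled alike.

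The cost is wording in the protocol, CRF and SAP, with no added subjects or visits. The HEMOBLAST upper limit may be slightly less favourable than a pooled one.

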7.3 Reporting

A serious adverse event (SAE) is defined as an adverse event that:

- Led to death;
- Led to a serious deterioration in the health of the subject, that either resulted in a life-threatening illness or injury, or a permanent impairment of a body structure or a body function, or in-patient hospitalization or prolongation of existing hospitalization, or resulted in medical or surgical intervention to prevent life-threatening illness or injury or permanent impairment to a body structure or a body function; or

A serious adverse device effect (SADE) is defined as an adverse device effect that has resulted in any of the consequences characteristic of a serious adverse event or that might have led to any of these consequences if suitable action had not been taken or intervention had not been made or if circumstances had been less opportune.

An unanticipated [serious] adverse device effect (UADE/USADE) is any serious adverse effect on health or safety, any life-threatening problem or death caused by, or associated with a device, if that effect, problem, or death was not previously identified in nature, severity, or degree of incidence in the protocol; or any other unanticipated serious problem associated with a device that relates to the rights, safety, or welfare of subjects.

All SAEs, SADEs, and UADEs must be reported to the Sponsor representative within 24 hours of the Principal Investigator becoming aware of it.

There are two methods of reporting. The first is to complete and save the Serious Adverse Event eCRF within 24 hours of the Principal Investigator becoming aware of the SAE, SADE, or UADE.

The second method of reporting is to contact the Sponsor representative for event reporting:

Contact Name: [name]

[contact] hour availability)
E-Mail: [contact]

The Principal Investigator should institute appropriate therapeutic and follow-up measures in accordance with good medical practice and record them in the subject's source documentation and on the Adverse Event CRF. It is the responsibility of the Principal Investigator to inform the appropriate personnel as required by IRB policy.

For SAEs that are unresolved, the Principal Investigator will continue to follow the event to resolution per standard medical care. Serious adverse event follow-up information regarding resolution will be provided to the Sponsor representative until the subject completes the 6 week follow-up and is discontinued from the clinical investigation. If the subject is discontinued prior to resolution of the event, the Principal Investigator will continue to follow the event until the event is deemed medically stable or resolved. Follow-up information after subject discontinuation will not need to be provided to the Sponsor representative.

For SADEs and UADEs, the event will be followed until resolution and follow-up information will be provided to the Sponsor representative.

7.4 Regulatory Authority and Institutional Review Board Notifications

The Sponsor shall report results of their evaluations of UADEs to the FDA, all reviewing IRBs, and all participating Investigators within 10 business days after the Sponsor/Sponsor representative first receives notice of the event.

Further, the Sponsor shall report results of their evaluations of UADEs to the Regulatory Authority and all applicable reviewing IRBs, and all participating Investigators within 10 business days after the Sponsor/Sponsor representative first receives notice of the event.

Please see Tables 10 and 11 below for reporting requirements and associated timelines.

